**Figure 4: OptiTrack Camera**

**Figure 5: Trackable**

## 1.5 Rationale for Study Design

As explained in the previous sections, conventional palliative radiotherapy for bone metastases offers only often modestly effective treatments that subject the patients to repeated visits to the treatment center and consume precious time and energy for ill patients and their families. With the STAT RT workflow, we hypothesize that we can offer more effective palliative treatments that are more efficient to plan and deliver, minimize toxicity, and require fewer total treatments. We are conducting this investigator initiated prospective pilot clinical trial to 1) evaluate the effectiveness and patient satisfaction with STAT RT for patients with painful bone metastases, and 2) optimize those components of the workflow needed to create a 30 minute Scan-Plan-Treat STAT RT workflow. Further development for this workflow has federal funding via a three- year 2012 CMS Innovation Challenge Award .

**Primary specific aim:** Quantify the time for pain relief, amount of pain relief, opioid use reduction, functional scores, quality of life, and satisfaction of patients treated with STAT RT for osseous metastases.

The objective of palliative treatment is to relieve pain, improve function, and improve quality of life. These will be measured before and after treatment with the following endpoints:

- The Brief Pain Inventory (BPI) is a proven survey to evaluate pain levels of patient's with metastatic bone pain and their responses to treatment (57).
- Patients will keep an analgesic use logbook and have their doses converted into Oral Morphine Equivalent Doses (OMED). In this way we can track changes in their opioid requirements.
- Treatment response will be measured by the guidelines set forth by the International Bone Metastases Consensus Group (58). They have established a method to measure response to palliative RT accounting for opiate use. These responses are categorized as: Complete Response, Partial Response, Pain Progression, Stable Pain. See Section 6.1.1 for details about this categorization.
- The FACT-G and FACT-BP questionnaires are proven measures of quality of life for people with painful bone metastases (59).
- Karnofsky Performance Score (KPS) is a proven measure of functional status.

We hypothesize that the convenience of the STAT RT workflow will result in high patient satisfaction. The FACIT-TS-BTCSQ survey has been shown to be an effective tool in measuring the satisfaction in patients being treated for metastatic bone disease (59). Therefore, we have modified this tool to suit our patient population, and we will use this survey to measure patient satisfaction at each assessment.

Toxicity will be assessed by CTCAE Version 4.0 and RTOG Late Radiation Morbidity Scoring Criteria. These are common criteria used to assess the toxicity associated with radiation therapy. The CTCAE will assess acute toxicity, and the RTOG Late Radiation Morbidity Scoring Criteria will assess late toxicity, which is defined as toxicity that occurs 3 months or more after treatment.

**Secondary Specific Aim:** Optimize the integration of commercially available and in-development software to develop the Scan-Plan-Treat STAT RT workflow.

As described in the background, this optimization will require:

- 1) rapid co-registration of diagnostic images onto MVCT simulation images for accurate contouring and treatment planning
- 2) real-time patient-specific quality assurance using CT detectors during treatment delivery
- 3) real-time patient motion tracking to ensure accurate patient setup during MVCT simulation and treatment delivery.

To implement rapid co-registration of diagnostic images onto MVCT simulation images into the workflow, we must first confirm that this image and contour-transferring method is just as accurate as the conventional method. Again, the experimental method requires rigid and deformable co-registration of

pre-contoured diagnostic image sets to MVCT simulation scans; and in the conventional method, pre-contoured diagnostic image sets are co-registered to kilovoltage CT (kVCT) simulation images, and then kVCT simulation images are co-registered to the MVCT scan. **See Figure 4.** Contours generated from these two different registration flows will be quantitatively compared as described in detail in Section 7.1.

Earlier we described the advantages of using the CT detector on the TomoTherapy unit with dose verification software to provide near real time 3D dose verification. We must confirm that the use of the CT detector and dose verification software yields equivalent results to conventional phantom-based quality assurance. Thus, exit radiation dose measurements and back-projected dose recalculation verification software will be compared to standard pretreatment phantom quality assurance measurements. If we prove the doses calculated by both methods to be equivalent, we could rely on only the CT detector and dose verification software for quality assurance in the future, which would further streamline the workflow.

As described in the background and preliminary studies, our in-house infrared tracking system has been developed to monitor patient positioning during simulation and treatment delivery. This infrared tracking system will be validated by 10 healthy volunteers and then used to monitor patient motion during treatments at the Emily Couric Cancer Center. The effectiveness of the infrared tracking system will be determined by comparing its position calculations with the position changes as determined by the position of the treatment set up lasers with respect to the patient's set up skin marks before and after treatment. Patient tracking is an additional experimental quality assurance process that in no way affects the patient's treatment and will not be implemented at Culpeper Regional Hospital at this time.

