### **5. Novel CT-detector-based quality assurance methodology**

Current standard of care TomoTherapy quality assurance methodology requires that each patient-specific treatment plan be delivered to a cylindrical plastic phantom with ion chamber and film measurement or an array of radiation detectors to ensure geometric and dose accuracy to within  $\pm 3\%$ . However, this method does not measure the dose that the patient is receiving during treatment or provide full 3D dose verification. It causes another delay in delivering the first treatment to the patient as it requires approximately 30-40 minutes to complete, and is generally done by a medical physicist after clinical patient care is finished. A methodology to monitor the patient exit dose in real time would increase patient safety through verification of daily treatment accuracy as well as expedite the treatment workflow. Clearly, a real-time quality assurance methodology that does not require moving the patient off the TomoTherapy treatment couch for phantom measurements is essential for the development of a 30-minute Scan-Plan-Treat workflow. Current dose verification methodologies measuring dose at the time of patient treatment are limited to point measurements on the patient surface (44), which is rarely in the target volume or a critical OAR, or though

expensive implanted dosimeters (45, 46) which are not practical for most palliative patients. Since there is not a method to directly measure the three dimensional dose in the patient, alternative approaches are being developed and tested in academic clinical settings. These alternative approaches reconstruct the delivered three dimensional dose distribution based on the measurement of either entrance or exit dose and back-projecting the measurements onto simulation or image guidance CT image sets.

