**Table 2: Critical Structures Dose Constraints**

| Organ                            | Volume               | Total Dose      |
|----------------------------------|----------------------|-----------------|
| Spinal cord                      | Any point            | 18 Gy maximum   |
| Esophagus                        | Any point            | 27 Gy maximum   |
| Ipsilateral brachial plexus      | Any point            | 24 Gy maximum   |
| Heart                            | Any point            | 30 Gy maximum   |
| Trachea and ipsilateral bronchus | Any point            | 30 Gy maximum   |
| Right and left lung              | <10% of volume       | 20Gy or greater |
| Liver                            | >700 cc normal liver | <15 Gy          |
| Single kidney                    | > 66% of volume      | <15 Gy          |
| Total Kidney Volume (L+R)        | < 35% of volume      | ≤15 Gy          |
| Stomach                          | Any point            | 30 Gy maximum   |
| Bowel                            | Any point            | 30 Gy maximum   |

- **Documentation requirements:** We will provide a dosimetry form that specifies the dosemetric criteria for the PTVs and OARs have been met for each study subject. This will ensure dosimetric compliance with PTV and OAR specifications. The treating radiation oncologist must sign this form for the study to continue.
- **RT Quality Assurance:** Standard quality assurance will be performed with all treatment plans. This involves the placement of a phantom with an array of radiation detecting ion chambers called OmniPro Matrixx on the couch of the TomoTherapy unit. The planned treatment is then delivered to theMatrixx phantom, and the ion chamber array ensures that the correct point dose and geometry is delivered. This ensures that the patient will get the dose as it was planned. Then, while the phantom and then the patient are irradiated, the fluence of the radiation exiting the patient will be measured by the CT detector. The exit dose verification software will then back-project this data collected by the CT detector onto the planning CT scan for volumetric or 3D dose reconstruction. This calculated 3D doses delivered will then be compared to the measured dose recorded by the phantom and also compared to the planned dose.

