**c) Exit Radiation Dose Verification**

In-development software provided by TomoTherapy Inc.® will be used to measure the exit dose fluence, backproject this fluence as entrance fluence, and then calculate the patient dose on the MVCT scan. This software will be further optimized and refined on this clinical trial. All patients' radiation treatment plans will undergo standard of care phantom-based quality assurance measurements. The phantom exit dose will also be calculated via this software in this optimization process. By comparing the values obtained with the software to the calculated treatment plan and phantom measurements, we hope to optimize this novel radiation dose verification software to +/- 3% calculated to delivered dose. Preliminary data shows that we are already at +/- 5% calculated to delivered dose (53).

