### **7.3 Data Analyses Plans**

Treatment response as defined by International Bone Metastases Consensus Group will be determined for each patient. As described in Section 6.1.1, pain intensity as defined by the BPI and opiate use as quantified by the OMED will be used to categorize patients as having: Complete Response, Partial Response, Pain Progression, Stable Pain. At each evaluation, the patient's BPI and OMED at that visit will be compared to the pre-treatment levels. The "Worst Pain" score from the patient's BPI will be used to evaluate for treatment response. Patient response does not require a statistical analysis. The percentage of patients in each response category at each evaluation will be reported.

Patient pain will be recorded using the BPI before treatment and at designated evaluations after treatment. Pain scores before and after treatment will be compared using a Wilcoxon signed ranks test to determine if there is a statistically significant difference. Example: Pre-treatment vs. 1 week, Pre-treatment vs. 4 weeks, etc.

Analgesic use will be recorded by requiring each patient to keep a logbook of their analgesic intake. Their opiate intake for the last 72 hours will be converted to OMED at each evaluation and used in the categorization of treatment response. The difference between their OMED before and after treatment will be compared using paired two-sample t-tests.

Patients' functional status will be determined using the Karnofsky Performance Scale at each evaluation. The difference between the KPS before and after treatment will be compared using a Wilcoxon signed ranks test.

Patients' quality of life will be measured using FACT-BP and FACT-G scores at each evaluation. The difference between the FACT scores before and after treatment will be compared using a Wilcoxon signed ranks test.

Patient satisfaction will be measured using a modified version of FACT - TS – BTCSQ. No statistical analysis will be required for reporting the results. The average scores from the satisfaction survey will be reported.

To evaluate the CT detector dose calculations, the delivered radiation dose obtained using the phantom quality assurance will be compared to the exit radiation dose quality assurance calculation. The calculated dose and delivered dose for each patient will be compared using a paired two-sample t-test, and the % difference in dose will be reported.

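### Dose agreement on deliveries expected to be correct does not show that the exit-dose software would catch a wrong one, so it cannot by itself support dropping phantom QA

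*Combined protocol and SAP*

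**What the plan says.** Section 1.5 sets a condition and draws a consequence from it. The condition is "If we prove the doses calculated by both methods to be equivalent"; the consequence is that "we could rely on only the CT detector and dose verification software for quality assurance in the future". No equivalence margin is given there.

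On phantom QA, Section 7.1(2)(c) states that "All patients' radiation treatment plans will undergo standard of care phantom-based quality assurance measurements". Section 1.3.9, item 5, describes this check as serving "to ensure geometric and dose accuracy to within" +/- 3%. The RT Quality Assurance bullet of Section 4.2 adds: "This ensures that the patient will get the dose as it was planned".

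On the software, Section 7.1(2)(c) gives the aim as "we hope to optimize this novel radiation dose verification software to +/- 3% calculated to delivered dose" and the present position as "Preliminary data shows that we are already at +/- 5% calculated to delivered dose". Exit fluence is recorded while the phantom is irradiated and again while the patient is treated (Section 4.2). The software output is compared with both the phantom measurement and the plan.

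On analysis, Section 7.3 states: "The calculated dose and delivered dose for each patient will be compared using a paired two-sample t-test". It adds that the percentage difference will be reported. Nothing else is planned for this objective (2.2.1).

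The infrared tracking system is treated differently. In Section 7.1(2)(d) it is tested against deliberate couch movements of 1 to 5 mm.

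**The concern.** A QA method exists to detect a wrong delivery. Close agreement on correct deliveries is necessary for that, but not sufficient: the method must also depart from the plan when the delivery does. Section 1.5 moves from agreement to sole reliance without that second step. No output, leaf or position error is introduced for the exit-dose software, and neither Section 7.1(2)(c) nor Section 7.3 asks how often an error would be flagged or how often a correct delivery would be flagged in error.

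The false-alarm side matters too. Section 1.3.9, item 5, itself acknowledges that a discrepancy in the reconstructed dose may come from the machine or may be an artifact of changes in the patient.

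At stake is a later decision about a safety check. If the trial reports a non-significant t-test and differences within 3%, a reader who follows Section 1.5 could take the case for dropping phantom QA as made.

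**Working it through.** **The plan's own figure.** The documents give no sample-size calculation for this aim. The only one is N = 21 for the pain score (Section 7.2). It reproduces: standardized change 2/3, two-sided alpha 0.05, and Wilcoxon efficiency 3/pi under a normal distribution give n = 21 with power 0.808. It says nothing about the QA aim. The planned 30 patients are used below, with one plan per patient assumed.

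**Step 1: goal against tolerance.** Write phantom dose = plan x (1 + e). A plan that passes phantom QA has |e| <= 3% (Section 1.3.9, item 5). Suppose a program always returns the plan. Its difference from the phantom, as a percentage of plan, is -e, so it lies within 3% on every passing plan; its difference from the plan is 0. It therefore meets the +/- 3% goal of Section 7.1(2)(c) by construction. This is an identity, not an empirical finding. Its use is to show that meeting the goal does not demonstrate sensitivity to error.

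**Step 2: the planned t-test on the same program.** The documents do not give the mean offset or SD of phantom against plan, so both are assumed. Errors are normal, truncated at +/- 3%; n = 30; 20,000 simulated trials. The table shows the share of trials with a non-significant t-test.

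| Mean offset | SD 0.5% | SD 1% | SD 1.5% | SD 2% |
|---|---|---|---|---|
| 0 | 95% | 95% | 95% | 95% |
| 0.5% | 0.1% | 25% | 65% | 83% |
| 1% | 0% | 0.1% | 13% | 50% |

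The t-test responds to the mean offset of the phantom from the plan. Whether it exposes such a program depends on a quantity unrelated to error detection.

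**Step 3: plans that fail phantom QA.** No text excludes them. For an assumed failure rate f, the expected number is 30f and the chance of none is (1 - f)^30.

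| f | Expected among 30 | Chance of none |
|---|---|---|
| 1% | 0.3 | 74% |
| 2% | 0.6 | 55% |
| 5% | 1.5 | 21% |
| 10% | 3.0 | 4% |

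If 3 failures occurred and all 3 were flagged, the one-sided 95% lower bound for the detection rate would be 0.05^(1/3) = 37%. With 1 to 3 failing plans kept in (off by 5 or 10%; the rest with no offset and SD 1%), the plan-returning program still gives a non-significant t-test in 81 to 99% of trials. With 1 to 3 targets per patient there could be up to 90 plans, hence 0.9 to 9 expected failures, still without a planned detection measure.

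**Step 4: can the data already planned do better?** Yes, in part. A program that returns the plan has software-minus-plan equal to 0 everywhere, so relating software-minus-plan to phantom-minus-plan exposes it. Take phantom SD 1% truncated at 3%, n = 30, and a program that tracks the phantom with added noise. The power to show a non-zero slope (two-sided 0.05) is then about 1.00, 0.90 and 0.52 at noise SD 1, 1.5 and 2.5%. This tests tracking within the tolerance, not detection of errors beyond it.

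**Step 5: a known-error test.** If all of 30 altered records are flagged, the exact two-sided 95% lower limit is 0.025^(1/30) = 88%. That is the best case; 29 of 30 gives 83%.

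**The case against.** The strongest reply is that this is a pilot whose stated objective (2.2.1) is to optimize and compare. Section 1.5 is conditional and speaks of the future, phantom QA is retained (Study Overview), and the 30-minute workflow is not used in this protocol (Section 1.4). Leaving error-injection work to later commissioning is a legitimate order of work. All of that stands. It limits the point to what may be concluded, but it does not repair the step from dose equivalence to sole reliance.

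A reader might also infer stronger things that the documents do not support:

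- *That the software is assessed only on plans that have already passed phantom QA.* The detector also records the phantom delivery itself, and no failing plan is excluded. Nor does the phantom check screen the patient deliveries (at least 30 x 2 = 60 and up to 30 x 5 = 150 with one target each), where deviations could arise. But the phantom measurement is made before treatment, so it gives no independent confirmation of an error on the day.
- *That the study cannot fail.* The software is reported at +/- 5% against a goal of +/- 3%. If +/- 5% means two SDs (an assumption; SD 2.5%), the chance that all 30 patients fall within 3% is 0.770^30, or about 0.04%; at SD 1.5% it is 0.954^30, about 25%.
- *That a plan-returning program would pass.* This is certain only for the +/- 3% goal on passing plans. No formal pass rule exists, and Step 2 shows that the t-test can reject such a program. The program is also hypothetical, since the real software works from measured fluence.
- *That no change of statistic would help.* Step 4 shows that one would, in part.

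Finally, Sections 1.3.9 and 1.4 describe leaf-opening checks from exit data and independent measurement of machine output and gantry angle. These are relevant to catching errors, but no known-error test is planned for them either. The preliminary data (24 patients, 347 fractions) are likewise reported as concordance.

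**Conclusion.** The concern holds as a limit on inference. The plan can describe how closely the software agrees with phantom and plan on deliveries expected to be correct. It cannot estimate how often the software would flag a wrong delivery or raise a false alarm, so equivalence of doses would not by itself justify relying on the software instead of phantom QA. The paired t-test adds a second weakness: failing to find a difference is not evidence of equivalence, and no margin is stated.

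The coincidence of goal and tolerance at 3% rests on the documents alone, reading the tolerance as phantom dose against plan. The counts of failing plans rest on assumed failure rates of 1 to 10% and one plan per patient. The t-test and tracking results rest on assumed offsets and SDs. The main conclusion depends on none of these assumptions, because no detection measure is planned at any failure rate.

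A reader might infer that trial patients are exposed to an unproven check. The documents do not support that: standard QA is done for every plan and the software does not replace it. This is something the sponsor should correct before the results are interpreted, not a safety defect of the trial.

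**What to change.** 1. **Section 1.5.** Restate the conclusion: agreement in this pilot supports further development of the software and does not by itself support relying on it in place of phantom QA. This costs nothing.
2. **Section 7.3.** Report the relation of software-minus-plan to phantom-minus-plan, with limits of agreement, on the data already being collected. The cost is a small amount of analysis time.
3. **Section 7.1(2)(c), only if the replacement claim is kept.** Add a test on phantom exit-detector records altered with known output, leaf-open-time and position errors spanning the 3% tolerance, mixed with unaltered records, with the analyst blinded to which are which. Report detection and false-alarm rates with exact 95% intervals.

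Item 3 needs some physics analysis time, but no patient exposure and no extra visits. It assumes that stored detector records can be altered and reprocessed in the supplied software, which the documents do not confirm. Altered records also test the software and not the detector chain, and the report should say so.

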## **1.6 Correlative Studies**

Not Applicable

## **2.0 STUDY OBJECTIVES**

### **2.1 Primary Objectives**

Our primary objectives are to quantify outcomes of patients with osseous metastases treated via the STAT RT workflow. Specifically, we are plan to:

- 2.1.1** Estimate the response to palliative radiation as defined by International Bone Metastases Consensus Group using the BPI and OMED to categorize into Complete Response, Partial Response, Pain Progression, and Stable Pain after receiving treatment via the STAT RT workflow.
- 2.1.2** Estimate the change in the patient's quality of life and function as scored by FACT-BP and KPS after receiving treatment via the STAT RT workflow.
- 2.1.3** Estimate patient satisfaction with the STAT RT workflow using a modified FACIT-TS-BTCSQ survey.
- 2.1.4** Report the treatment-related toxicity using CTCAE Version 4 and RTOG Late Radiation Morbidity Scoring Criteria after receiving treatment via the STAT RT workflow.

